After eligibility is determined and baseline data are collected, parents will be randomized, in two cohorts, to the treatment or materials-only control condition. Given the relatively small sample size in each cohort at each site ($n = 30$ at each of three sites), simple randomization is not recommended as it might result in unequal group sizes. We will use 1:1 block randomization within each site to give an equal number of subjects in each group. To ensure balance of important covariates, we will block on our key moderators: whether the youth has an intellectual disability (ID) and is in high school. Co-occurring ID and being in vs. out of high school impact service eligibility, and ID impacts the likelihood of PSE and community employment. By balancing moderators, we maximize our power to detect effect modification of the treatment effect; and we minimize the chance of having a very extreme distribution of important (moderating) covariates.

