Power/Sample Size: We plan to recruit 180 subjects and expect to retain 152 through the 12-month follow-up (76 per cohort). For power calculations, we consider baseline to post-test changes. For continuous outcomes, the size of effect that we will have 80% power to detect will be impacted by the correlation between the pre and post measurement of the outcome. At worst ($r=0$), we will have 80% power to detect a 0.46 sd difference in continuous outcomes. If the correlation is 0.2 or 0.4 we will be able to detect a 0.29 or 0.17 sd difference, respectively. We believe these estimates are conservative because, from our pilot work, correlations between baseline and post-test scores of intervention targets were 0.56 (empowerment), 0.39 (advocacy skills), and 0.57 (knowledge). For binary outcomes, the probability of being employed or in PSE was about 0.5 in pilot data; under this assumption we will have 80% power to detect a relative risk of 1.44. For Aim 4, we will have 80% power to detect a 0.42 sd modification of the treatment effect assuming a $r=0.2$. All calculations assume a two-sided significance level of 0.05. The power to detect **mediation effects** were made using the MedPow package in R. For the power calculation, we considered moderate associations between (1) VAP-T and the mediator ($r_{X,M}=0.3$), (2) Mediator and outcome, controlling for VAP-T ($r_{M,Y|X}=0.25$), (3) VAP-T and outcome controlling for the mediator ($r_{X,Y|M}=0.1$) using a fixed sample size of 152 ($\alpha=0.05$). Under these assumptions, we have 83% power to detect the indirect effect of VAP-T on the outcome through the mediator.

9. Privacy/Confidentiality Issues

IRB approval will be obtained prior to the initiation of the project. All project staff will be highly experienced in working with these populations, will have completed University mandated Human Subject Research Ethics training, and will be instructed in procedures for ensuring participant rights and confidentiality.

To protect confidentiality of participants, we will separate names and contact information from all other data. Participant codes, rather than names, will be used to index all data. Contact information, including names, must be maintained during this longitudinal study as participants must be scheduled for follow-up visits and all data files must be linked. Consent, contact information, and information linking participant identity with participant codes will be stored separately from all coded data.

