Advocating for Supports to Improve Service Transitions (ASSIST)

NCT04173663

Statistical Analysis Plan

Document Date: 06/01/2022

STATISTICAL DESIGN AND POWER

Effects of the Intervention: Aims 1 and 2: Generalized linear models will be used to estimate the effect of treatment group assignment on each of the outcome variables considered. All models will include an indicator variable for treatment group and a treatment by time interaction while controlling for site and sex to improve the precision of the treatment effect estimate. We choose to model site as a fixed effect (2 d.f.) rather than a random effect because there are too few sites to have a stable estimate of a random effects variance.

For **Aim 1**, continuous outcomes (empowerment, advocacy skills, advocacy activities) will be modeled using linear regression and ordinal outcomes (knowledge) will be modeled using proportional odds ordinal logistic regression. The proportional odds model generalizes the non-parametric Wilcoxon rank sum test to a regression setting and is applicable to a wide variety of outcome types. However, we will consider parametric models for count data including Poisson and Negative Binomial regression if appropriate. In these cases, sensitivity analyses will be conducted to evaluate if our conclusions are robust to the choice of regression model.

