Missing Data. An advantage to our proposed random effects longitudinal models is that they will readily incorporate both missing waves of data and mistimed measurements. In general, we will assume that data are missing-at-random (MAR) for the growth models and missing completely at random (MCAR) for binary and ordinal outcome models estimated using GEE and mediation analysis. Attrition analysis will be used to evaluate these assumptions. Analysis methods will also consider subjects who fail to complete the study (“dropouts”). Indirect information about the dropouts will be obtained by using binary logistic models to predict the probability of dropping out on the basis of all baseline predictor variables. When a variable is a significant predictor of dropout, the distribution of that variable differs for completers and subjects who drop out.

Power/Sample Size: We plan to recruit 180 subjects and after dropout expect to retain 162 subjects through initial post-test (Aim 1) and 152 subjects (76 per treatment group) through the 12-month follow-up (Aims 2 - 4). For power calculations, we consider baseline to post-test changes using the smaller sample size of 152. For continuous outcomes, the size of effect that we will have 80% power to detect will be impacted by the correlation between the pre and post measurement of the outcome. At worst ($r=0$), we will have 80% power to detect a 0.46 sd difference in continuous outcomes. If the correlation is 0.2 or 0.4, we will be able to detect a 0.29 or 0.17 sd difference, respectively. We believe these estimates are conservative because, from our pilot work, correlations between baseline and post-test scores of intervention targets were 0.56 (empowerment), 0.39 (advocacy skills), and 0.57 (knowledge). For binary outcomes, in pilot data, the probability of being employed or in PSE was about 0.5, so under this assumption we will have 80% power to detect a relative risk of 1.44. Regarding Aim 4, we will have 80% power to detect a 0.42 sd modification of the treatment effect assuming a $r=0.2$. All calculations assume a two-sided significance level of 0.05.

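### The stated 80% power for 0.29 SD (r=0.2) and 0.17 SD (r=0.4) does not follow from 76 per arm; actual power is about 44% and 21% at best with one post-test, and the Aim 4 figure is unsupported for the two binary key moderators

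*SAP*

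**What the plan says.** The Power/Sample Size paragraph of the SAP fixes the basis of the calculation: "For power calculations, we consider baseline to post-test changes using the smaller sample size of 152". It gives 76 per treatment group, 80% power and a two-sided 0.05 level. At r=0 the detectable difference is put at 0.46 SD and called the worst case. The SAP then says: "If the correlation is 0.2 or 0.4, we will be able to detect a 0.29 or 0.17 sd difference, respectively". The Protocol, section 8 (Statistical Considerations), has the same: "we will be able to detect a 0.29 or 0.17 sd difference, respectively".

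The SAP adds: "We believe these estimates are conservative because, from our pilot work, correlations between baseline and post-test scores" of the intervention targets were 0.56, 0.39 and 0.57.

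For effect modification the SAP says "we will have 80% power to detect a 0.42 sd modification of the treatment effect" at r=0.2, and the Protocol agrees: "For Aim 4, we will have 80% power to detect a 0.42 sd modification of the treatment effect". Neither gives the type of moderator or its distribution. The Randomization text in Protocol section 4 says: "we will block on our key moderators: whether the youth has an intellectual disability (ID) and is in high school". Both of these are yes/no variables.

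The analysis model is in the SAP under Aims 1 and 2: "All models will include an indicator variable for treatment group and a treatment by time interaction while controlling for site and sex". Continuous outcomes get a random intercept. No baseline covariate is named.

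**The concern.** A pre-post correlation of 0.2 removes very little variance, yet the stated detectable difference falls from 0.46 to 0.29 SD. At r=0.4 it falls to 0.17 SD, little more than a third of the r=0 value. Neither adjusting for baseline nor taking a change score gives a gain of that size.

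Apart from the separate mediation calculation, these are the only detectable-effect figures for the continuous outcomes, which include empowerment, advocacy skills, advocacy activities and social participation. A reader who accepts 80% power for 0.17 to 0.29 SD could take a null result as evidence against effects that the stated two-wave calculation would miss more than half the time. Calling the figures conservative adds to that risk. Aim 4 is exploratory and all its interactions will be reported, so the harm there is limited to an unsupported statement of sensitivity.

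**Working it through.** **Inputs.** From SAP, Power/Sample Size: N=152, 76 per arm, two-sided 0.05, 80% power, r=0, 0.2 and 0.4, pilot r=0.39, 0.56 and 0.57. From Protocol section 4: 1:1 allocation and two binary key moderators. Assumptions: SD means the SD of the outcome, equal at baseline and follow-up; the moderator splits are also assumed, since the documents give none.

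**The plan's r=0 figure.** The noncentral t at 76 per arm gives a detectable difference of 0.457 SD, so 0.46 is reproduced (power 80.4%). This is a comparison of follow-up means.

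**Effect of r with one baseline and one post-test.** Multiply 0.457 by √(1−r²) if baseline is a covariate, or by √(2(1−r)) for a change score.

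| r | Stated | Baseline-adjusted | Change score |
|---|---|---|---|
| 0 | 0.46 | 0.457 | 0.647 |
| 0.2 | 0.29 | 0.457 × 0.980 = 0.448 | 0.457 × 1.265 = 0.579 |
| 0.4 | 0.17 | 0.457 × 0.917 = 0.419 | 0.457 × 1.095 = 0.501 |
| 0.39 (pilot) | – | 0.421 | 0.505 |
| 0.56 (pilot) | – | 0.379 | 0.429 |
| 0.57 (pilot) | – | 0.376 | 0.424 |

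The SAP's own model (treatment, time, treatment by time, compound symmetry, baseline and post-test) gives 0.643, 0.575 and 0.498 at r=0, 0.2 and 0.4 by the normal approximation. It is therefore equivalent to the change analysis. On that basis 0.46 SD at r=0 has 51% power.

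**Power at the stated differences.**

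| Setting | 0.29 SD, r=0.2 | 0.17 SD, r=0.4 |
|---|---|---|
| 76 per arm, baseline-adjusted | 44% | 21% |
| 76 per arm, change | 29% | 16% |
| 81 per arm (162 at post-test), adjusted / change | 47% / 31% | 22% / 17% |
| 90 per arm (no dropout), adjusted / change | 51% / 33% | 24% / 18% |

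Reaching 80% would take 181 and 458 per arm (adjusted) or 300 and 653 (change). With 76 per arm it would take r of about 0.77 to 0.80 for 0.29 SD and 0.93 for 0.17 SD. The highest pilot r is 0.57.

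**Other readings tried.**
- SD taken as the SD of the change score: 43% and 18%.
- One-sided 0.05: at most 57% and 31%.
- Post-test and 12-month data together, assuming compound symmetry and a constant effect. Baseline-adjusted, the variance factor is (1+r)/2 − r², which gives 0.342 and 0.336 SD, with power 66% and 29%. Under the SAP's treatment-by-time model, the detectable differences are 0.498 and 0.431 SD, with power 37% and 20%.
- Unlimited follow-up waves at r=0.4, baseline-adjusted: 0.457 × √(0.4 − 0.16) = 0.224 SD, still above 0.17.

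The stated values coincide with 0.46 × (1−r)²: 0.46 × 0.64 = 0.294 and 0.46 × 0.36 = 0.166. That is not a valid SD reduction. It is an inference about the source of the error, and nothing here depends on it.

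**Aim 4 (r=0.2, N=152, normal approximation).** With k=√0.96 (adjusted) or √1.6 (change), and a proportion p of families in one level of the moderator, the standard error of a treatment-by-binary-moderator interaction is k × 2/√(152·p(1−p)). For a continuous moderator, per SD, it is k × 2/√152. The detectable interaction is 2.80 standard errors.

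| Moderator | Detectable, adjusted / change | Power at 0.42 SD, adjusted / change |
|---|---|---|
| Binary 50/50 | 2.80 × √(4/38) × √0.96 = 0.89 / 1.15 | 26% / 17% |
| Binary 30/70 | 0.97 / 1.25 | 23% / 15% |
| Continuous, per SD | 2.80 × 2/√152 × √0.96 = 0.445 / 0.575 | 75% / 53% |

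The stated 0.42 also coincides with 0.64 times the detectable difference inside one subgroup of 38 per arm (0.64 × 0.651 = 0.417). That would not be an interaction test.

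**The case against.** The arithmetic cannot be rescued, but its reach can be disputed.

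- **Timing and consequence.** The SAP is dated June 2022, after the intervention groups had been scheduled to finish. The 180 families are planned directly and not derived from 0.29 or 0.17 SD. Correction changes no model, alpha level or decision rule. This stands, and it is why the remedy is only wording. It does not make the printed power correct.
- **Scope.** The figures concern continuous outcomes only. Employment/PSE is binary and has its own figure, a relative risk of 1.44, which is reproduced (0.50 versus 0.72, power 80.0%). Knowledge and number of services are ordinal. This stands.
- **The worst-case figure.** A cautious reader can rely on 0.46 SD. Baseline-adjusted, it has 86% to 93% power at the pilot correlations, so it is conservative on that basis. On change it has 85% to 86% at r=0.56 to 0.57 but only 72% at 0.39. The conservative claim therefore needs qualifying for 0.46 SD, and it fails for 0.29 and 0.17 SD.
- **Change basis.** The r=0 figure of 0.46 suggests that the sponsor did not compute a change score. That is fair, so the baseline-adjusted results come first. But the SAP names change, and its model as written is equivalent to it.
- **More waves.** The planned analysis is longitudinal, and empowerment and advocacy skills are measured at both post-test and 12 months. Using both raises power for 0.29 SD to 66% if baseline is adjusted for. It stays below 80%, and 0.17 SD remains out of reach.
- **Aim 4.** Several listed moderators may be continuous, and for those 0.42 SD per SD is near the mark when baseline is adjusted for. The objection to 0.42 therefore applies only to the two binary moderators.

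**Conclusion.** The concern holds. At 76 per arm and two-sided 0.05, the statements of 80% power for 0.29 SD at r=0.2 and 0.17 SD at r=0.4 are wrong in both documents. The conclusion assumes equal SDs at the two times and one post-test, as the SAP's stated basis implies. Extra follow-up waves narrow the gap for 0.29 SD but cannot bring 0.17 SD within reach under compound symmetry.

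At the pilot correlations the detectable difference is 0.38 to 0.42 SD adjusted, or 0.42 to 0.51 SD on change, so 0.29 and 0.17 SD are optimistic. For the two binary key moderators, 0.42 SD is too small by a factor of at least two: the 50/50 split is the most favourable case and gives 0.89 SD adjusted. The point must be corrected because the stated power is not what the design delivers. Confidence in the arithmetic is high.

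**What to change.** In Protocol section 8 and in the Power/Sample Size paragraph of the SAP:

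1. Name the analysis and the waves that the power refers to.
2. Replace the figures at r=0, 0.2 and 0.4 with the matching set. For two-wave change or treatment-by-time, as the SAP now reads, these are 0.65, 0.58 and 0.50 SD. For baseline adjustment they are 0.46, 0.45 and 0.42 SD, and the SAP model must then name the baseline covariate. If the power is to refer to more than two waves, state the correlation structure and effect pattern assumed.
3. Replace the conservative claim with the detectable difference at the pilot correlations: 0.42 to 0.51 SD (change) or 0.38 to 0.42 SD (adjusted). Keep the pilot correlations in the text.
4. Restate Aim 4 by moderator type and assumed split. For example, a 50/50 binary moderator gives about 0.89 SD adjusted or 1.15 SD change, and a continuous moderator about 0.45 or 0.57 SD per SD. Say that only large interactions are detectable for the two binary key moderators.

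The cost is wording in two documents. Sample size and alpha are unchanged, and the model changes only if the sponsor chooses to add baseline adjustment. The stated sensitivity becomes less favourable.

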The ASSIST program is a 12-week advocacy training to educate parents of youth with ASD about the adult service system. It is a group training, comprised of didactic instruction, family-sharing activities, case studies, and group discussions. Due to social distancing restrictions during the COVID-19 pandemic, the intervention will be conducted via web-conferencing. The ASSIST program for the proposed study will be directed at each site by an experienced Program Facilitator from the community with knowledge about group processes, person-centered planning, and adult service systems, who will be coached by a member of the study team. The ASSIST program will be delivered in full partnership with the local disability community. In most sessions, the Program Facilitator will be aided by community content experts who present the specifics of each topic. Experts will include representatives from the Parent Training and Information Centers, The Arc, the University Centers for Excellence in Developmental Disabilities, various

government agencies, attorneys, and parents of individuals with ASD. We have tentatively identified (and partially recruited) most of these community experts at each project site.

Finally, we take further steps to ensure that parental advocacy reflects the goals of the youth with ASD by: having a semi-structured discussion with the youth with ASD and their supporters about that youth's hopes, dreams, and goals prior to their parent taking the ASSIST program; developing individualized goals for transition outcomes from those discussions that will be used as an outcome measure; and including the youth with ASD in follow-up data collection to incorporate their perspective.

Specific Aims

Specific Aim 1. To use a multi-site RCT to examine whether ASSIST participation increases the intervention target of parent advocacy ability (defined by parental knowledge about adult service systems, advocacy skills, empowerment, and advocacy activities).

Hypothesis. Relative to a materials-only control group, ASSIST participation will lead to improvements in parental knowledge about adult services, advocacy skills, empowerment, and advocacy activities.

Specific Aim 2. To test whether participating in ASSIST leads to increases in employment, PSE, social participation, and access to services that facilitate these activities (number of services, unmet service needs, barriers), for youth with ASD transitioning from high school to young adulthood.

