1.0 Study Procedures

All data collection will occur in years 2019-2023 as explained below:

- Enrollment for the project is expected to occur in years 1-2.
- Cohort 1 (C1) Intervention group will take ASSIST from February-August 2020 (IL and TN sites; includes COVID break) and August-November 2020 (WI sites)

- C1 Control group will take ASSIST September-November 2021 (TN and IL Sites) and January-March 2022 (WI Site)
- Cohort 2 (C2) Intervention group will take ASSIST from August-Nov 2020 (TN and IL Sites) and November 2020-February 2021 (WI site)
 - C2 control group will take ASSIST from February-April 2022 (TN and IL) and March-May 2022 (WI sites).

Note: Due to social distancing restrictions, the in-person intervention series that began in February 2020 was paused between Spring 2020 to Summer 2020 for Cohort 1 intervention groups (TN and IL). In response to continued pandemic regulations, ASSIST was moved to synchronous web-conferencing in Summer 2020, and this method was the mode of delivery for all remaining sessions and series at all sites (TN, IL, WI)

A comprehensive characterization of each participant's circumstances and family context will be completed by administering a battery of direct assessments and informant report measures during the baseline visit. This visit will include structured observations, psychological testing, structured interviews, and questionnaires/surveys. Note that some of the survey measures will be offered to participants as web-links to be filled out at home or at the lab if social distancing restrictions allow. Paper copies of all surveys will be available based on participant preference.

Follow-up data collection points (post-intervention, 6, 12, 18, 24, and 30 months) may take place online or over the phone, depending on participants' preference and the included measures to be collected for that time-point. We will also make alternate methods of data collection available to youth with ASD for the interview, including video/text/online chat, as some participants with ASD may be more comfortable answering questions via chat than over the phone or web conference. The table of measures included in the *Procedures for Enrolled Families* section of this protocol, shows the longitudinal measures follow-up schedule for parent and youth participants.

5. Procedures

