The power to detect mediation effects were made using the MedPow package in R^{82,83}. For the power calculation, we considered moderate associations between (1) VAP-T and the mediator ($r_{X,M}=0.3$), (2) Mediator and outcome, controlling for VAP-T ($r_{M,Y|X}=0.25$), (3) VAP-T and the outcome controlling for the mediator ($(r_{X,Y|M}=0.1)$ using a fixed sample size of 152 ($\alpha=0.05$). Under these assumptions, we have 83% power to detect the indirect effect of VAP-T on the outcome through the mediator.

Additional Analyses. In addition to these key analyses, we will conduct descriptive analyses to inform future research and development of the VAP-T. For example, we will carefully examine the attendance data to determine whether there is a number of sessions that seems necessary to benefit from the VAP-T, whether any particular sessions seem to be more important, and if accessing a greater proportion of sessions outside of the group format (i.e., at home, online) limits effectiveness. Analyses will include (but not be limited to) examining frequencies, medians, and means on intervention target scores for those who attended (vs. missed) each session and examining the distribution of outcome variables by the number of sessions in which content was accessed in the group format and by any format (in-person and online combined). We will also perform variable clustering and redundancy analysis by examining the correlation among the potential attendance predictors. We will work closely with our biostatistician to identify appropriate inferential statistics if these initial analyses appear informative to the further development of the VAP-T program.

BIBLIOGRAPHY

82. Cohen J. *Statistical power analysis for the behavioral sciences*. 2nd ed. Hillsdale, N.J.: L. Erlbaum Associates; 1988.

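### The SAP's attendance analysis counts online access as outside the group format, although the live group itself moved online, so the comparison as written would mostly reflect site, cohort and calendar period

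*SAP*

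**What the plan says.** The SAP, marked "Document Date: 06/01/2022", says under Additional Analyses that "we will conduct descriptive analyses to inform future research and development of the VAP-T". One of its questions is "if accessing a greater proportion of sessions outside of the group format (i.e., at home, online) limits effectiveness". It would be examined by describing outcomes according to the number of sessions "accessed in the group format and by any format (in-person and online combined". Together, the two phrases equate group format with attending in person and put everything online on the other side.

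The protocol describes a different delivery. Section 2 presents ASSIST as group training and says that, because of the pandemic, "the intervention will be conducted via web-conferencing". The Study Procedures section says that "ASSIST was moved to synchronous web-conferencing in Summer 2020" and that "this method was the mode of delivery for all remaining sessions and series at all sites (TN, IL, WI"). It also says that the series begun in person in February 2020, for the Cohort 1 intervention groups in Tennessee and Illinois, was paused from spring to summer of that year.

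**The concern.** The analysis asks a practical question: does reaching the content outside the live group weaken the program? For that, the exposure must separate families who took part in the live group from those who obtained the content some other way.

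As worded, it separates in-person from online. From Summer 2020 the live group was online, so a family present at every live web session would be recorded as having had no group-format sessions. That family would fall in the same category as one that reached the content individually. In-person sessions were possible only in certain series, so the exposure is largely fixed by where and when a family was enrolled. A difference in outcomes along this variable could come from site, cohort, pandemic phase or the interrupted first course as easily as from format.

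What is at stake is the guidance for further development of the program. The SAP also allows inferential statistics to follow if the descriptive results look informative.

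**Working it through.** **Planned numbers.** Section 3 of the protocol gives 3 sites × 2 cohorts × 30 families = 180, which reproduces the stated total. The Randomization text gives 1:1 allocation within site, so 180/2 = 90 intervention families and 30/2 = 15 per site-by-cohort series.

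**Delivery by series**, from the Study Procedures schedule:

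| Intervention series | Scheduled | Live delivery | Planned families |
|---|---|---|---|
| TN, Cohort 1 | Feb–Aug 2020, with break | in person, then web | 15 |
| IL, Cohort 1 | Feb–Aug 2020, with break | in person, then web | 15 |
| WI, Cohort 1 | Aug–Nov 2020 | web | 15 |
| TN, Cohort 2 | Aug–Nov 2020 | web | 15 |
| IL, Cohort 2 | Aug–Nov 2020 | web | 15 |
| WI, Cohort 2 | Nov 2020–Feb 2021 | web | 15 |

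Web only: 15 + 45 = 60 families, and 60/90 = 67%. Some in-person sessions: 15 + 15 = 30 families. In-person exposure therefore exists in 2 of 6 series. Wisconsin has none. In Tennessee and Illinois it changes with cohort, and in Cohort 1 it changes with site.

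**How much of the exposure is set by series.** Let f = 30/90 = 1/3 be the fraction of families in a mixed-format series, k the number of in-person sessions before the pause, and p the attendance rate. The documents give neither k nor p, so both are assumed over a range. Web-only families all score zero. With attendance independent from session to session, the variance of in-person sessions attended splits into:

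- between mixed-format and web-only series: f(1 − f)(kp)²
- within the mixed-format series: f·k·p(1 − p)

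The between-series share is (1 − f)kp / [(1 − f)kp + (1 − p)].

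- k = 2, p = 0.6: 0.80/(0.80 + 0.40) = 67%
- k = 4, p = 0.8: 2.13/(2.13 + 0.20) = 91%
- k = 10, p = 0.9: 6.00/(6.00 + 0.10) = 98%

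The SAP question is framed as a proportion. A simulation of the proportion of content accessed outside in-person sessions (k = 2 to 8, attendance 60% or 80%, and 0% to 100% of missed sessions made up) gave a between-series share of 65% to 98%.

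Independence between sessions is favourable to a high share. At the opposite extreme, where each family attends all or none of the in-person sessions, the within part becomes f·k²·p(1 − p) and the share is (1 − f)p / [(1 − f)p + (1 − p)]. That is 0.40/0.80 = 50% at p = 0.6 and 0.60/0.70 = 86% at p = 0.9.

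**What remains within series.** In the two mixed-format series, the in-person sessions were the early ones. Even there, format is tied to session topic and to the pause.

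**The case against.** The strongest reply is that the SAP never formally defines group format as a variable; it only glosses the term in a parenthesis. Read beside a protocol that calls ASSIST group training and its web delivery synchronous, a sensible analyst could code a live web session as the group session, and the problem would not arise. That is possible, but the SAP does not say it. Contrasting group format with in-person and online combined points the other way. The SAP is also dated after the last intervention series was due to end, in February 2021, so the change in delivery was already known.

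The second reply is about reach, and it stands. The analysis is additional, descriptive and given as an example. No model or test is specified, and neither the Aim 1 and 2 comparisons nor the Aim 3 mediation analysis uses this variable. The other attendance summaries, by session and by any format, do not depend on the split. A pile-up of zeros would also be visible in the planned distributions. The redundancy analysis among attendance predictors is only a partial safeguard, because it does not mention site or cohort.

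A reader might go further and infer that the analysis carries no information about format. The documents do not support that: Cohort 1 families in Tennessee and Illinois could miss in-person sessions, so some within-series variation remains. Nor do they support a claim that the program would be steered in a particular wrong direction, because no direction of bias can be derived from them.

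**Conclusion.** The concern holds as an inconsistency between a stated coding rule and the delivery the protocol describes. Coded as written, about 60 of 90 planned intervention families have zero group-format sessions whatever their live attendance. Most of the variation in the exposure lies between series: 65% to 98% over the ranges tried with attendance independent between sessions, and no less than half in the all-or-none extreme at 60% attendance or more. Live web attendance is also merged with individual access, so the question the SAP asks cannot be answered.

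The family counts are planned figures with equal allocation in every series; actual numbers per series are not given. The variance shares rest on assumed numbers of in-person sessions and assumed attendance. The consequence is confined to a descriptive analysis, and a reader should not infer any threat to the randomised comparisons in Aims 1 and 2.

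**What to change.** In the SAP's Additional Analyses:

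- count live sessions as group format, whether in person or by synchronous web-conference;
- define access outside the group format as content reached other than in the live session, as far as the attendance data distinguish it;
- make that comparison within site-by-cohort series;
- report any description of in-person versus web delivery as confounded with site, cohort, calendar time and the pause.

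No separate contrast of treatment effects between the mixed-format series and the others is needed. The SAP did not plan one, and it would carry the same confounding.

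The wording change is small. The cost is precision, with about 15 intervention families per series. Feasibility is also open: session dates separate the in-person period from the web period, but they do not separate live web attendance from individual access. The documents do not say whether that was recorded. If it was not, the SAP should say that the question cannot be answered for web sessions.
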